8.2. Screening and Critical Baseline Assessments

Screening assessments are outlined in the Time and Events Table, (Section 8.1). The following demographic parameters will be captured: year and month of birth, sex, race and ethnicity.

Medical/medication history will be assessed as related to the inclusion/exclusion criteria listed in Section 6.

Written informed consent must be obtained prior to performance of any study related procedures. Screening can take place over multiple days.

8.3. Study Assessments and Procedures

8.3.1. Physical Exams

A complete physical examination will include, at a minimum, assessment of the Cardiovascular, Respiratory, Gastrointestinal and Neurological systems and skin. Height will also be measured and recorded at screening only and weight at screening and baseline only.

A brief physical examination will include, at a minimum, assessments of the skin, Respiratory, Cardiovascular system, and abdomen (liver and spleen).

8.3.2. Vital Signs

Vital signs will be measured in a supine position and will include temperature, systolic and diastolic blood pressure and pulse oximetry.

8.3.3. Electrocardiogram (ECG)

ECGs will be measured in a supine position.

Twelve-lead ECGs will be obtained during the study using an ECG machine that automatically calculates the heart rate and measures PR, QRS, QT, and QTcF intervals. Refer to Section 6.8.2 for QTcF criteria and additional QTcF readings that may be necessary.

8.3.4. Clinical Safety Laboratory Assessments

All protocol required laboratory assessments must be conducted in accordance with a study manual or Laboratory Manual, and Protocol Time and Events Table (Section 8.1). Laboratory requisition/order forms must be completed, and samples must be clearly labelled with the participant number, protocol number, site/center number, and visit date. Details for the preparation and shipment of samples will be provided by the laboratory and are detailed in the study manual or the laboratory manual. Investigators will also

refer to their local institution for samples being analysed by the local laboratory. Reference ranges for all safety parameters will be provided to the site by the laboratory responsible for the assessments.

If additional non-protocol specified laboratory assessments are performed at the institution's local laboratory and result in a change in participant management or are considered clinically significant by the Investigator (e.g., SAE or AE or dose modification) the results must be recorded.

Central laboratory results will be prioritized except where specific test results are not available due to sample hemolysis as specified in the Time and Events (Section 8.1). In these instances, results from site local laboratories will be collected in the eCRF.

Laboratory sample parameters are listed below:

Hematology

	RBC Indices:	Automated WBC Differential:
Platelet Count		
Red Blood Cell (RBC) Count	Mean corpuscular volume (MCV)	Neutrophils
White Blood Cell (WBC) Count (absolute)	Mean corpuscular hemoglobin (MCH)	Lymphocytes
Reticulocyte Count	Mean corpuscular hemoglobin concentration (MCHC)	Monocytes
Hemoglobin		Eosinophils
Hematocrit		Basophils
Haptoglobin		

Clinical Chemistry

Blood urea nitrogen (BUN)	Potassium	AST (SGOT)	Total (TBL) and direct bilirubin
Creatinine	Chloride	ALT (SGPT)	Uric Acid
Total Protein	Total carbon dioxide (CO ₂)	Gamma glutamyltransferase (GGT)	Albumin
Sodium	Calcium (corrected)	Alkaline phosphatase (ALP)	Lactic acid dehydrogenase (LDH)
Serum complement (CH50, C3)	Immunoglobulin M (IgM)	Immunoglobulin A (IgA)	Immunoglobulin G (IgG)
HbA1c			
Fasted labs			
Glucose (fasted) Week 1 and Week 13 only	Insulin (fasted) Week 1 and Week 13 only		


Lipid Panel (fasted) Week 1, Week 13, Final Follow up/Early Withdrawal only
	
Total cholesterol Triglycerides HDL cholesterol LDL cholesterol (calculated using Martin-Hopkins equation) Cholesterol/HDL ratio Non-HDL cholesterol (calculated) CRP/ High sensitivity CRP

---	---

NOTE: Details of Liver Chemistry Stopping Criteria and Follow-Up Procedures are given in Appendix 2: Liver Safety Required Actions and Follow up Assessments.

Routine Urinalysis

Specific gravity, pH
glucose, protein, blood and ketones by dipstick
Microscopic examination (if blood or protein is abnormal)
Microalbumin/creatinine ratio at baseline, week 13, week 20 (if urine protein is abnormal)

Other tests

QuantIFERON®-TB Gold
Viral Serology [HIV1/HIV2, Hepatitis B (HBsAg), Hepatitis B (Core antibody), Hepatitis C (Hep C antibody)]
Vaccine titers for: tetanus, diphtheria, Hepatitis A, Hepatitis B, Pneumococcal
FSH (as needed for confirmation of postmenopausal status)
Pregnancy Tests: serum test at screening, Week 20, and early withdrawal and urine dipstick pre-dose at other timepoints. Positive urine tests should be confirmed with a serum test.

All laboratory tests with values that are considered clinically significantly abnormal during participation in the study should be repeated until the values return to normal or baseline. If such values do not return to normal within a period judged reasonable by the Principal Investigator, the etiology should be identified, if possible and the Sponsor notified.

8.3.5. Pharmacokinetics

Blood samples for PK analysis of RVT-1401 will be collected at the time points indicated in Section 8.1, Time and Events Table. The actual date and time of each blood sample collection will be recorded.

Processing, storage and shipping procedures are provided in the study manual or lab manual.

Serum analysis will be performed under the control of the Sponsor. Concentrations of RVT-1401 will be determined in serum samples using the currently approved bioanalytical methodology. Raw data will be archived at the bioanalytical site.

8.3.6. Anti-Drug Antibody (ADA) and Neutralizing Antibody (NAb)

Blood samples for ADA and NAb analysis will be collected at the time points indicated in Section 8.1, Time and Events Table. The actual date and time of each blood sample collection will be recorded.

Processing, storage and shipping procedures are provided in the study manual or lab manual.

ADA analysis will be performed under the control of the Sponsor. Anti-RVT-1401 antibody titers will be determined in serum samples using the currently approved bioanalytical methodology. Raw data will be archived at the bioanalytical site. If anti-RVT-1401 antibody titers are detected, they will be further characterized using a validated NAb assay.

Participants with treatment emergent positive results (change from baseline) for anti-RVT-1401 antibody at Week 20 will be requested to return at approximately 6, 9, and 12 months post-dose for additional samples or until their result is no longer positive. However, for purposes of safety follow-up and database lock participation ends at the Week 20 visit.

8.3.7. Pharmacodynamics

Blood samples for PD analysis will be collected at times indicated in the Time and Events Table (Section 8.1).

[figure not shown]
Pharmacodynamic Markers

Total IgG, and differentiation by class: IgG subclasses (IgG1, 2, 3, and 4)
--

The actual date and time of each blood sample collection will be recorded. These samples may be used for the analysis of exploratory biomarkers. Samples will be collected, labelled, stored, and shipped as detailed in the study manual or lab manual.

8.3.8. Exploratory Biomarkers

Blood samples for exploratory biomarker analysis will be collected at times indicated in the Time and Events Table (Section 8.1).

The actual date and time of each blood sample collection will be recorded. The timing of samples may be altered and/or samples may be obtained at additional time points to

ensure thorough biomarker assessment. Samples will be collected, labelled, stored, and shipped as detailed in the study manual or lab manual.

8.4. Rating Scales & Questionnaires

8.4.1. Functional Assessment of Chronic Illness Therapy-Fatigue (FACIT-F) Scale

The FACIT-F scale is a validated scale which measures the physical, emotional and social implications of fatigue, one of the key clinical manifestations of warm autoimmune hemolytic anemia [Acaster, 2015; Webster, 2003]. Scores range from 0-52, with a higher score indicating a higher quality of life. A score of less than 30 would indicate severe fatigue. The scale takes approximately 5-10 minutes to complete.

8.4.2. Medical Research Council (MRC) Breathlessness Scale

The MRC Breathlessness scale is a questionnaire that consists of five statements about perceived breathlessness. The focus of the scale is to quantify the disability associated with breathlessness and not the severity of the breathlessness [Stenton, 2008]. This scale has undergone iterations with the current Modified MRC Subject Version, ranging from Grade 0 (limited to no disability) to Grade 4 (severe disability). This scale has been used in patients with chronic obstructive pulmonary disease (COPD), where the researchers further stratified on patients with low hemoglobin levels. Their data demonstrate that anaemic COPD patients had significantly higher MRC [Ferrari, 2015]. The scale can be self-administered by asking subjects to choose a phrase that best describes their condition. The score is the number that best fits the patient's level of activity. A score can usually be obtained in less than a minute.

8.4.3. EQ-5D-3L Scale

The EQ-5D-3L is a validated measurement of health-related quality of life [Devlin, 2018; Hernandez, 2018]. The scale consists of 2 components, the EQ-5D descriptive system and the EQ visual analogue scale. The descriptive system evaluates mobility, self-care, usual activities, pain/discomfort and anxiety/depression. The scale can be self-administered by subjects who select the most appropriate statement within each category. A lower score corresponds to better quality of life. The EQ VAS records the patient's self-rated health on a vertical visual analogue scale where the endpoints are labelled 'Best imaginable health state' (100) and 'Worst imaginable health state' (0). The patient can select any number from 0-100. Completion of both components of the scale can be performed in under 5 minutes.

8.4.4. Satisfaction Questionnaire

A brief survey asking participants for feedback on their experience with the SC injections during the course of the study will be completed at the end of the treatment period. The survey will take less than 2 min to complete by the participant.

9. DATA MANAGEMENT

For this study, participant data will be entered into a Sponsor-approved electronic database and combined with data provided from other sources (e.g., safety laboratory, PK and PD vendor, etc.) in validated datasets then transmitted electronically to the Sponsor or designee.

Management of clinical data will be performed in accordance with applicable Sponsor approved standards and data cleaning procedures to ensure the integrity of the data, e.g., removing errors and inconsistencies in the data.

Adverse events and concomitant medications terms will be coded using Medical Dictionary for Regulatory Activities (MedDRA) and the World Health Organization Drug Dictionary Enhanced (WHO-DDE), respectively.

The Principal Investigator will retain original source documents and the Sponsor will receive eCRF-required data as electronic datasets. Participant initials will not be collected or transmitted to the Sponsor.

10. STATISTICAL CONSIDERATIONS AND DATA ANALYSES

10.1. Sample Size Considerations

The sample size for this study was not determined using statistical methods. The sample size was chosen based on clinical and recruitment considerations for this Phase 2 study.

10.2. Statistical Considerations

10.2.1. Analysis Populations

Intention-To-Treat (ITT) Population

All enrolled participants who take at least one dose of study medication will be included in the ITT population. Participants will be summarized by treatment group.

This will be the population for all PD parameters.

Safety Population

All participants who enroll in the study and receive at least one dose of study treatment will be included in the Safety Population. Participants will be summarized by actual treatment group.

This will be the population for the safety analyses, as well as for presentation and summarization of baseline/demographic characteristics.

Pharmacokinetic Population

The PK Population will include all participants who undergo PK sampling and have evaluable concentration-time data for analysis.

Pharmacodynamic Population

The PD population will include all participants who have baseline measure, along with a post baseline measure and receive at least one dose of study treatment.

10.3. Analysis

Final analysis will be performed after the completion of the study and the database is locked.

Data will be listed and summarized. Treatment will be assigned based on the dosing schedule and included in the data listings. Listings will be sorted by participant, day, and time; summaries will be presented by treatment, day, and time.

Unless stated otherwise, descriptive summaries for continuous variables will include n, mean, standard deviation (SD), median, first and third quartiles, minimum, and maximum. The geometric mean with associated 2-sided 95% confidence interval (CI), and the between-participant CV (%CVb) for PK parameters only will also be included. For categorical variables, n and percent will be used as summary statistics. Baseline is the last available assessment prior to time of the first dose unless it is specified otherwise. If there are multiple assessments collected on the same scheduled time, the average of these assessments will be used. For tabulated safety summaries, only the scheduled assessments will be included in the summary tables.

Version 9.4 or higher of the SAS system will be used to analyze the data as well as to generate tables, figures, and listings.

Complete details will be documented in the Statistical Analysis Plan (SAP), which will be signed off prior to the lock of the study database.

10.3.1. Baseline Demographics and Characteristics

Subjects baseline demographics and characteristics will be summarized by the treatment groups, and by overall.

10.3.2. Primary Endpoint for Efficacy

The primary endpoint will be defined as the proportion of responders at Week 13. The Fisher's exact test will be used for the difference between the two treatment groups.

The analysis of the primary endpoint will be performed on ITT based on all available data, without using any imputation method for missing data.

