3.3. Rationale

3.3.1. Study Rationale

The purpose of the current study is to assess the efficacy and safety of RVT-1401 in the treatment of WAIHA that is worsening or refractory in spite of therapy with steroids and or immunosuppressants or worsening with steroid or immunosuppressant taper. Results from this study will be used to inform dosing and to support progression into a Phase 3 study.

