4. OBJECTIVE(S) AND ENDPOINT(S)

Objectives	Endpoints
Primary	

To examine the effect of RVT-1401 on proportion of responders (defined as Hb level $\geq 10\text{g/dL}$ with at least a $\geq 2\text{ g/dL}$ increase from baseline without rescue therapy or blood transfusions in the previous two weeks)
 
To assess the safety and tolerability of RVT-1401 in subjects with WAIHA
	
Proportion of responders at week 13
 
Assessment of safety and tolerability by analysis of adverse event (AE) data and changes from baseline in vital signs, ECGs, and clinical laboratory values

Secondary	

To examine the effect of RVT-1401 on change in Hb levels
	
Change from baseline in Hb levels

To examine the effect of RVT-1401 on time to response
	
Time to response

To examine the effect of RVT-1401 on change in hematocrit levels
	
Change from baseline in hematocrit levels

To examine the effect of RVT-1401 on proportion of participants with Hb levels in the normal range
	
Proportion of participants with Hb levels in the normal range at week 13

To examine the effect of RVT-1401 on time to achieving Hb levels in the normal range
	
Time to achieving Hb levels in the normal range

To examine the effect of RVT-1401 on change in fatigue
	
Change from baseline in FACIT-F score

To examine the effect of RVT-1401 on change in dyspnea
	
Change from baseline in Medical Research Council (MRC) breathlessness scale

To examine the effect of RVT-1401 on change in health-related quality of life
	
Change from baseline in EQ-5D-3L score

To assess the change in serum levels of total IgG & IgG subclasses (I-IV)
	
Change from baseline in levels of total IgG & IgG subclasses (I-IV)

To examine RVT-1401 PK following repeated doses in patients with WAIHA
	
Concentration of RVT-1401 pre-dose (C_{trough})

To assess the changes in LDH, bilirubin,
	
Change from baseline in LDH, bilirubin, and

haptoglobin
 
To measure anti-RVT-1401 antibodies following repeated doses in patients with WAIHA
	
haptoglobin
 
Immunogenicity determined by change from pre-dose in anti-RVT-1401 antibodies, and characterization of any anti-RVT-1401 to confirm neutralization potential

Exploratory
	
	

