5. STUDY DESIGN

5.1. Overall Design

This is a Phase 2, non-randomized, sequential, open-label study to investigate the safety, tolerability, PK, PD, and efficacy of RVT-1401 (680 mg/weekly and 340 mg/weekly) in patients with WAIHA. The study design is illustrated in Section 5.2.

[figure not shown]
Two cohorts of participants will be enrolled in a non-randomized sequential approach. Participants will be enrolled into Cohort 1 (680 mg/weekly) first followed by Cohort 2 (340 mg/weekly). In the Phase I healthy volunteer study, both dosing regimens were well tolerated (Section 3.3.3). Since 680 mg/weekly has the greater likelihood of demonstrating clinical efficacy, this dosing regimen will be studied in Cohort 1.

Following the initial dose at the Baseline Visit (Week 1, Day 1), study visits will occur weekly throughout the treatment period. Following the final dose at Week 12, visits will occur weekly through Week 14 and then at Week 16 and Week 20. Safety, PK, PD, and clinical assessments will be collected throughout the study. Refer to Section 8.1, Time and Events Table.

Optional home visits will be offered to collect (at a minimum) blood samples, vital signs, and to review adverse events and concomitant medications.

Each participant will participate in the study for up to approximately 24 weeks: up to a 4-week screening period, a 12-week treatment period, and an 8-week follow up period.

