6. PARTICIPANT POPULATION

6.1. Type and Number of Participants

A sufficient number of participants will be enrolled to achieve approximately 16 evaluable participants. Enrollment is competitive.

In order to manage the total study enrollment, the Sponsor may suspend screening and/or enrollment at any site or study-wide at any time.

If participants prematurely discontinue the study, additional replacement participants may be enrolled at the discretion of the Sponsor.

Deviations from inclusion and exclusion criteria are not allowed because they can potentially jeopardize the scientific integrity of the study, regulatory acceptability or participant safety. Therefore, adherence to the criteria as specified in the protocol is essential.

To determine participant eligibility at screening, a single repeat of certain tests such as laboratory values or ECGs is allowed at the discretion of the Principal Investigator.

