6.9.2. Management of Rescue Therapy

Rescue therapy during the first 8 weeks of the Treatment Period is permitted for participants with haemoglobin levels <7.0 g/dL or in the presence of signs/symptoms of myocardial ischemia, hypoxia, or TIA/stroke. Participants requiring rescue therapy after the Week 8 visit will be discontinued and an early withdrawal visit scheduled.

Blood Transfusion

The date, time, and number of units transfused should be recorded, along with the results of cross-match testing. Follow-up hemoglobin should be measured with 12 hours of the end of the transfusion. Hemoglobin values will be censored from efficacy analyses for the 2 weeks following a blood transfusion.

Prednisone/Prednisolone

Prednisone/prednisolone rescue (up to a 50% increase from baseline for up to 5 days), is permitted as per the rescue therapy guidelines (Section 6.9.2). The date, time, and dose should be recorded. Hemoglobin values will be censored from efficacy analyses for the 2 weeks following the last dose of prednisone/prednisolone rescue.

Dexamethasone

High dose dexamethasone (up to 40 mg daily for up to 4 days) is permitted as per the rescue therapy guidelines (Section 6.9.2). The date, time, and dose should be recorded. Hemoglobin values will be censored from efficacy analyses for the 2 weeks following the last dose of dexamethasone rescue.

IVIg and Plasma Exchange

Due to the mechanism of action for RVT-1401, the use of IVIG and Plasma exchange are not allowed.

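### Protocol 10.3.2, read naturally, would drop late-rescue failures from the Week 13 responder denominator; the rate gets no interval, and the 10.3.3 model as listed cannot give per-visit differences

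*Protocol*

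**What the plan says.** Protocol Section 4 gives the primary efficacy objective as "To examine the effect of RVT-1401 on proportion of responders". A responder has haemoglobin of at least 10 g/dL and a rise of at least 2 g/dL, "without rescue therapy or blood transfusions in the previous two weeks".

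Section 10.3.2 specifies one inference: "The Fisher's exact test will be used for the difference between the two treatment groups". It uses the ITT set, which 10.2.1 defines as everyone enrolled and dosed, takes the data that are available and imputes nothing. Section 10.3 summarises categorical variables by count and percent; the confidence interval in that section is for PK parameters only.

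Section 6.9.2 on rescue: "Participants requiring rescue therapy after the Week 8 visit will be discontinued and an early withdrawal visit scheduled". It adds: "Hemoglobin values will be censored from efficacy analyses for the 2 weeks following a blood transfusion". The same two weeks apply after the last dose of steroid rescue.

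Section 10.3.3 bases percentages for categorical secondary endpoints on participants with a value at that visit. For continuous endpoints it names an MMRM or ANCOVA with treatment, visit and baseline, and promises a treatment difference with standard error, interval and p-value at every visit.

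On design and purpose: "Two cohorts of participants will be enrolled in a non-randomized sequential approach" (5.1) and "Results from this study will be used to inform dosing and to support progression into a Phase 3 study" (3.3.1). Section 10.3 leaves details to the SAP. SAP Version 3.0 (Sections 1 and 6.1) covers Cohort 1 only, 5 enrolled, and produces listings only.

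**The concern.** Three features of the text would weaken the efficacy result if the protocol analysis were run.

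- **Denominator.** The endpoint treats recent rescue as failure, but the rescue and missing-data rules together would tend to remove late-rescue participants from the calculation. The error runs one way: the response rate goes up. If late rescue is commoner on the lower dose, a real dose difference shrinks.
- **No estimate of precision.** A two-cohort test does not estimate how well the drug works. Because the cohorts are enrolled one after the other, any difference is also mixed with enrolment period.
- **Model.** Without a treatment-by-visit term, the difference promised at each visit is one number repeated.

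At stake is the use stated in 3.3.1: informing dose and supporting Phase 3.

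**Working it through.** The plan has no power figure or computed sample size to reproduce (Protocol 10.1). The documents give about 16 participants and no split, so 8 per cohort and all counts below are assumptions.

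**Step 1. Who can have had rescue in the two weeks before Week 13?** Rescue is permitted up to Week 8. The longest permitted course is 5 days of prednisone or prednisolone; with the two-week look-back that is 5 + 14 = 19 days. Week 8 to Week 13 is 35 days nominally, or 32 after visit windows of +1 and −2 days. Permitted rescue has therefore cleared by Week 13. Rescue after Week 8 leads to discontinuation and an early withdrawal visit. Haemoglobin is drawn at that visit, but no text maps it to Week 13, and within two weeks of rescue it is censored.

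**Step 2. What does 10.3.2 do with them?** It names no denominator. Scoring an absent Week 13 value as failure would be an imputation, which 10.3.2 rules out. The only denominator rule in the protocol, in 10.3.3 for secondary endpoints, uses observed values. The natural reading is that they drop out.

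**Step 3. Size.** Let n be treated, x responders, k late rescues and r = k/n. If nothing else is missing, the observed-case rate is x/(n − k) = (x/n)/(1 − r). For x = 4, n = 8, with exact (Clopper-Pearson) 95% intervals:

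| k | Rate | 95% CI | Factor |
|---|---|---|---|
| 0 | 4/8 = 50% | 15.7–84.3% | 1.00 |
| 1 | 4/7 = 57.1% | 18.4–90.1% | 1.14 |
| 2 | 4/6 = 66.7% | 22.3–95.7% | 1.33 |
| 3 | 4/5 = 80.0% | 28.4–99.5% | 1.60 |

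Between doses, take 6/8 (75%) on 680 mg and 3/8 (37.5%) on 340 mg, a gap of 37.5 points. Two late rescues on 340 mg give 3/6 = 50%, a gap of 25. Four, an extreme case, give 3/4 = 75%, a gap of 0; Fisher p moves from 0.31 to 1.0.

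**Step 4. What the Fisher test conveys.** 0/8 v 0/8 and 6/8 v 6/8 both give p = 1.0. The exact 95% intervals per cohort are 0–36.9% and 34.9–96.8%.

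**Step 5. The model as listed.** With terms visit + treatment + baseline, the treatment difference is a single coefficient at every visit. With complete data and equal visit weights (compound symmetry) it estimates the mean of the visit differences. Post-baseline haemoglobin visits up to Week 13 in the Time and Events Table are Weeks 2, 3, 4, 5, 7, 9, 11 and 13. Let D be the Week 13 difference.

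- Linear rise from 0 at Week 2: (0+1+2+3+5+7+9+11)/(8 × 11) = 38/88 = 0.43D.
- Rise to a plateau from Week 5: (0 + 1/3 + 2/3 + 5 × 1)/8 = 0.75D.
- Early gap, 2D at Weeks 2 to 5 and D from Week 7: (4 × 2 + 4 × 1)/8 = 1.5D.

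With AR(1) correlation of 0.3 to 0.9 the first two become 0.44–0.48D and 0.58–0.73D. The direction depends on the time course.

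**The case against.** - **No current analysis is affected.** This stands. SAP Version 3.0 only lists data for Cohort 1, and no text says the study will resume. A reader might infer that the Cohort 1 report carries a biased rate; it does not, since no rate is calculated there. Section 10.3 sends details to the SAP, and a resumed study would need new ones. But the protocol sentences would be their starting point, and Version 3.0 does not correct them.
- **10.3.2 does not state an observed-case denominator.** Correct. It says ITT, and the observed-value rule is written for secondary endpoints only. Rescue records are themselves available data. Nor does a two-week look-back make someone rescued at Week 9 or 10 a failure at Week 13. The removal is the natural reading, not an explicit rule.
- **A reader might infer that the rescue clause can never classify anyone at Week 13.** That goes too far: an early withdrawal visit could fall near Week 13, and the text does not settle whether it counts.
- **A reader might see replacement as a second route out of the denominator**, since 6.1 says: "If participants prematurely discontinue the study, additional replacement participants may be enrolled at the discretion of the Sponsor". A dosed participant who is replaced remains in ITT under 10.2.1, so this does not follow.
- **The interval follows from count and percent.** True, and the report would show whether both rates were low or high. The omission concerns what is presented as the main result.
- **Naming MMRM or ANCOVA may imply visit-specific estimates.** Possibly, but visit cannot be a term in an ANCOVA fitted at one visit, so the sentence needs repair on either reading. Nor does averaging always understate Week 13: 3.3.3.3 reports a faster IgG fall on 680 mg, so an early gap is plausible.

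**Conclusion.** The concern holds for Protocol 10.3.2 and 10.3.3, if the study resumes or the protocol analysis is run. The denominator is the main point. As written, late-rescue failures would most naturally drop out of the Week 13 rate and raise it by a factor of 1/(1 − r): 1.14 to 1.60 for one to three of an assumed 8. This rests on reading 10.3.2 with 6.9.2 and 10.3.3, and on taking discontinuation with an early withdrawal visit to mean no Week 13 value. The documents report no late rescue, so the actual size is unknown.

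The missing interval and the non-randomised comparison are matters of presentation, but they bear directly on the stated objective. The model sentence cannot give its promised output as listed; the error at Week 13 could go either way. All three should be corrected before any resumption.

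**What to change.** **10.3.2.** Replace the available-data sentence:

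- Denominator: all treated participants, except those curtailed by the sponsor's pause before Week 13, whose number is reported separately.
- Non-responders: in addition to those who fail the haemoglobin criteria, anyone discontinued for rescue or lack of efficacy, or whose Week 13 haemoglobin is censored for rescue.
- For values missing for any other reason, state the main rule in advance. Report two sensitivity analyses: observed cases, and all other missing counted as non-response.
- Main result: each cohort's Week 13 proportion with an exact 95% CI. Keep the Fisher p-value, labelled descriptive because the cohorts are sequential and non-randomised.

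The rescue rule itself is not at issue.

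**10.3.3.** Name the visits and add treatment-by-visit with a parsimonious covariance structure. An unstructured matrix needs 8 × 9/2 = 36 parameters for the visits to Week 13, or 11 × 12/2 = 66 with Weeks 14, 16 and 20, in about 16 people. Alternatively, state a separate ANCOVA (treatment, baseline) at each visit and remove visit as a term.

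**SAP Version 3.0.** No change to the Cohort 1 listings.

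Cost: protocol wording and minor programming, no extra participants. The downside is that wide intervals are shown openly and the reported response rate may be lower.
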